The secondary aim is to evaluate the effectiveness of treatment of snoring on the sleeping partner's sleep quality as measured by the *CGI-I* scale, the *Epworth Sleepiness Scale (ESS)*, and a modified *Symptoms of Nocturnal Obstruction and Related Events (SNORE-25)* questionnaire.

C3 Rationale for the Selection of Outcome Measures

Primary Outcome:

Clinical Global Impression of Improvement Scale (CGI-I) - Partner: To address the primary aim, the primary outcome measurement is the CGI-I Scale in the sleeping partner. The CGI-I will pose the question “Overall, how do you rate the response to snoring treatment?”, with 7 response options including: *Very Much Improved, Much Improved, Minimally Improved, No Change, Minimally Worse, Much Worse, and Very Much Worse*. The CGI-I is adapted from a previously validated measure commonly used in psychiatric studies, and is a self-report scale²¹. Participants will be measured after completing 4 weeks of their respective intervention. As snoring primarily effects the sleeping partner, the sleeping partner's responses will be the primary outcome measurement. A sleeping partner who rates the response to treatment as either *Very Much Improved* or *Much Improved* will be graded as a responder to treatment. The percentage of responders to non-responders will be compared between the two treatment arms.

Secondary Outcomes:

1. **CGI-Improvement Scale - Participant:** The CGI-I will be administered to the participant in the same method as described above.
2. **CGI-Severity (CGI-S) Scale - Partner and Participant:** The CGI-Severity Scale poses the question “On average, how much of a problem does your [partner’s] snoring pose?” The 5 response options will include: no problem, mild problem, moderate problem, severe problem, problem as severe as it can be. It will be measured both at baseline and after treatment. In addition, the CGI-S will be measured by the sleeping partner on a daily basis both before and after treatment.

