- Prior polysomnogram (PSG) within the past 60 months showing AHI < 5 and no more than 10% gain in body weight since the prior polysomnogram
- Possess a sleeping partner who sleeps in the same room as the participant for ≥ 4 nights a week and who can report outcomes
- Access to the internet
- Ability to follow up within 1 month after adequate fitting of MAD or 4 weeks of Mometasone

Inclusion criteria for the sleeping partner:

- Age ≥ 18
- Possess a sleeping partner who sleeps in the same room as the participant for ≥ 4 nights a week and who can report outcomes
- Access to the internet

2.b Exclusion Criteria

Individuals will not be allowed to participate in this study if they meet one or more of the exclusion criteria:

- Significant hypoxemia as defined as SaO₂ below 89% for $\geq 12\%$ of the total nocturnal monitoring time
- Inability to wear a MAD defined as missing more than 50% of their dentition or their dentition is not in good condition.
- Prior intolerance of MAD
- Current treatment for OSA
- Concurrent use of sedatives or > 2 alcoholic drinks per night
- Chronic nasal obstruction due to structural anatomic defects, nasal polyps, or history of unresponsiveness to nasal rinses.

Sleeping partners do not have any exclusion criteria defined for this study.

2.c Ethical Considerations

This study relies on participation of human subjects. Informed consent will be obtained in person for each participant at the baseline visit to ensure their safety, minimize risk, and ensure full confidentiality. All assessment will be conducted via HIPAA-compliant online surveys using REDCap. We are asking the participant to engage in an intervention; however, they are not the ones solely benefitting from it as their partner is also expected to benefit.

2.d Subject Recruitment Plans and Consent Process

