Informed consent will be obtained at the start of study visit prior to any research activity. To minimize the possibility of coercion or undue influence during the consent process, patients will be given the option to read through and sign the consent with the RC or alone. We will also remind the patient prior to the consent process that their ability to receive care will not be impacted by the presence or absence of consenting to the study, and that if they do consent, they can withdraw at any time. To minimize the coercion to finish the study, the participants will be reminded that if they do not finish the study, they will still be compensated on a pro-rated basis for the previously completed steps.

All assessments will be conducted either in person or virtually via HIPAA-compliant online surveys at baseline and then throughout the study course virtually or over the telephone.

2.e Randomization Method and Blinding

Participants will be randomized according to computer-generated code to receive either the mandibular advancement device or standard at-home therapy. [name] will provide the randomization table to the co-investigator, [name].

Due to the nature of the randomization process, blinding during the data collection phase will not be possible as the primary researcher will have to coordinate a specific initial visit with either the maxillofacial physician or [name], the otolaryngology specialist. Participants cannot be blinded either as the treatment modalities differ in a way which makes adequate blinding not possible. [name] will be blinded to randomization. Prior to data analysis, [name] will blind groups as “A” and “B” so that the team will not know which intervention corresponds to A and B throughout both the data analysis and manuscript writing process.

2.f Risks and Benefits

Mandibular Advancement Device. Risks of the Prosomnus sleep and snore device include drooling, temporomandibular disturbances, tooth pain, TMJ disturbances, and movements of the teeth that can change a person’s bite. All these risks are uncommon and resolve after cessation of use. These risks will be minimized using a morning

repositioning device each morning after the Mandibular Advancement Device is worn. Benefits of the device include a reduction in snoring intensity and severity.

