At the end of study, all the Visit 2 - End of Study outcome measures will be presented to the participant via REDCap. The End of Study measures include the CGI-I scales, the CGI-S scale, the ESS, and the SNORE-25 or modified SNORE-25. This will occur asynchronously through email surveys distributed through the Washington University REDCap server or through a scheduled telephone call depending on the participant's preference. Both the participant and the sleeping partner will complete this step. Participants will also return their compliance sheets at this time.

E7 Safety and Adverse Events

7.a Safety and Compliance Monitoring

The specific monitoring plan for this study is based on the potential risk of participation and size and complexity of the planned investigation. Based on these considerations, this study will have a monitoring committee comprised of [name], [name], and [name], the study biostatistician. All reports of a Serious Adverse Event (SAE) or an Unexpected Adverse Event (UAE) will be investigated by the monitoring team and reported to Washington University HRPO according to the reporting requirements.

Participants who experience serious adverse effects with therapy will be removed from the study. Participants with serious adverse effects will be instructed to call 911, seek immediate medical care and discontinue all further treatment.

7.b Definitions of Adverse Events

Adverse event (AE) means any untoward medical occurrence associated with the use of a drug in humans, whether or not considered drug related (21 CFR 312.32(a)).

An adverse event (also referred to as an adverse experience) can be any unfavorable and unintended sign (e.g., an abnormal laboratory finding), symptom, or disease temporarily associated with the use of a drug, without any judgment about causality or relationship to the drug.

An adverse event can arise from any use of the drug (e.g., off-label use, use in combination with another drug) and from any route of administration, formulation, or dose, including an overdose.

Serious adverse events (SAEs) are special cases of an adverse event where adverse outcomes are severe. SAEs include the following events:

- Death of any of the participants associated with a clinical trial.
- An event which can lead to life-threatening complications or put the life of participants at risk because of participation in a clinical trial.

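### E6 lets the partner's CGI-I, the primary outcome, be taken online or by telephone according to preference, with no rule on who calls and no record of the mode

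*Combined protocol and SAP*

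**What the plan says.** Section C3 states that "the primary outcome measurement is the CGI-I Scale in the sleeping partner". The scale is one question with seven options; C3 says it "is adapted from a previously validated measure commonly used in psychiatric studies, and is a self-report scale". The dichotomy is set there too: "A sleeping partner who rates the response to treatment as either *Very Much Improved* or *Much Improved* will be graded as a responder to treatment".

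On how the rating is collected, the sections differ:

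- **E6 (Visit 2)** offers two routes for the end-of-study measures, the CGI-I among them: "This will occur asynchronously through email surveys distributed through the Washington University REDCap server or through a scheduled telephone call". The choice is by preference ("through a scheduled telephone call depending on the participant's preference"), and E6 adds that snorer and partner both complete this step.
- **2.d (recruitment and consent)** also permits virtual or telephone assessment after baseline.
- **2.c (ethical considerations)** names one route: "All assessment will be conducted via HIPAA-compliant online surveys using REDCap".
- **E8 (outcome ascertainment)** likewise has snorers and partners complete the forms in REDCap.

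On blinding, section 2.e says that "blinding during the data collection phase will not be possible". Section 3.h has the Principal Investigator leave before randomisation, which the rest of the team then carries out. The A/B masking in 2.e and 3.h covers analysis and manuscript writing only.

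**The concern.** The primary endpoint is one global opinion about how well treatment worked. Typing that opinion into a form and speaking it to a member of the trial team are different measurement conditions, because a spoken answer is open to courtesy toward the listener and to the way the question is read out. If the listener knows the arm, the effect may also differ by arm.

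The plan does not fix the mode, name the caller, require a caller unaware of the arm, provide a script for this call, ask the partner to answer apart from the snorer, or record which mode was used. The last gap matters most: without that record, nobody could later show that the modes were balanced between arms, or examine the result if they were not.

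**Working it through.** **Inputs from the plan.** F1 gives 60 pairs randomised, 33% dropout, 20 evaluable per arm, a control responder rate of 30%, a hypothesised difference of 20 points (read as 30% against 50%), and a 95% margin of error of 30 points. C3 gives the responder cut: the top two of seven categories.

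**The plan's own figures.** Evaluable pairs: 60 × (1 − 0.33) = 40.2, or about 20 per arm. Wald half-width: 1.96 × √(0.3 × 0.7/20 + 0.5 × 0.5/20) = 1.96 × √0.023 = 0.297, or 29.7 points. The stated 30 is reproduced, and this point disputes no figure in F1.

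**Weight of one rating.** 1/20 = 5 points on that arm's responder rate. Two ratings in one arm make 2/20 = 10 points, half of the hypothesised 20. Only a change across the boundary between Minimally Improved and Much Improved counts; a move from No Change to Minimally Improved leaves the endpoint as it was.

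**When mode biases the comparison.** Let m be the share of partners rated by telephone in an arm, and e the change in the probability of a responder rating that a call produces. The shift in the difference (MAD minus control) is

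shift = m(MAD) × e(MAD) − m(control) × e(control).

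The documents give neither m nor e. The values below are assumptions that only show the range.

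| Telephone share, MAD / control | Effect of a call | Shift in difference |
|---|---|---|
| 30% / 30% | equal in both arms, 5 to 30 points | 0 |
| 50% / 30% | equal in both arms, 5 to 30 points | 0.20 × 5 to 0.20 × 30 = 1 to 6 points |
| 50% / 10% | equal in both arms, 5 to 30 points | 0.40 × 5 to 0.40 × 30 = 2 to 12 points |
| 50% / 50% | differs between arms by 10 to 20 points | 0.50 × 10 to 0.50 × 20 = 5 to 10 points |

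The bias therefore needs unequal use of the telephone, or an unequal effect of it. The plan rules out neither and collects nothing that would show either.

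**The sections side by side.** E6 and 2.d agree that the telephone is allowed. Section 2.c allows only online surveys. E8 could be squared with E6 if staff enter spoken answers into REDCap, but then the form is not self-completed, which sits badly with a scale that C3 says "is adapted from a previously validated measure commonly used in psychiatric studies, and is a self-report scale".

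**The case against.** The other side has a good deal in its favour.

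- **The partner is unblinded in either mode.** Someone who shares a bedroom with a person wearing a device or mouth tape knows the treatment. Expectation bias is built into the design, and the telephone can only add to it. This stands.
- **The telephone protects completeness.** F1 expects 33% dropout, and F4 plans no adjustment for missing data. A rule that loses ratings could do more harm than a mixed mode. This stands, and is why the telephone should remain as a fallback.
- **This is a pilot sized on feasibility**, with a 30-point margin of error. That limits the severity.

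A reader might also infer more than the text supports:

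- *That the caller certainly knows the arm.* E6 names no caller. Knowledge of the arm is an inference from 2.e and 3.h, and 3.h describes the Principal Investigator as blinded.
- *That the caller has built a rapport with the partner through the two-weekly check-ins.* Section 3.e places those check-ins with study participants and concerns their adherence. It does not mention partners.
- *That the snorer picks the mode after randomisation.* E6 does not say when the preference is taken, and 2.d counts partners among the participants, so the preference may be each respondent's own.
- *That online answers are private and telephone answers are overheard.* The documents say neither.
- *That the bias could reach 25 points.* If 25% of partners were called (an assumption), 5 of 20 ratings per arm would be exposed. A 25-point shift would need all five in one arm to cross the cut in the same direction and none in the other.

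What remains is narrower: the mode for the primary rating is uncontrolled and unrecorded, in a trial that says its data collection is unblinded.

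**Conclusion.** The point holds as a minor one. The plan allows two modes for its single primary rating, describes them inconsistently across 2.c, 2.d, E6 and E8, and has no safeguard on the caller and no record of the mode. The exposure is 5 points of an arm's responder rate for each partner moved across the cut, on the plan's own 20 evaluable pairs per arm. The documents give no direction or total size, and do not show that bias will occur. The illustrative shifts rest entirely on assumed telephone shares and mode effects. The case for acting is that the remedy is cheap and makes a possible imbalance visible. No sample-size figure changes.

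**What to change.** 1. In E6, make self-completion by the partner, through the partner's own REDCap link, the default for the CGI-I. It should be answered separately from the snorer and before any end-of-study call with staff. Internet access is already an entry criterion for both members of the pair (2.a), so the telephone is not needed as a routine route.
2. Allow the telephone only when the partner has not answered after reminders within a stated window. Use a fixed script read by an existing team member who, where possible, does not know the arm.
3. Record the mode in one REDCap field and report mode by arm beside the primary result.
4. Reword 2.c, 2.d, E6 and E8 so that all four describe the same procedure, and say in E6 whose preference counts and who enters the answers.

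The cost is protocol wording, one database field and one table, with no extra staff. The downside is a few more reminders and slightly later ratings from partners who would have preferred a call. Keeping the window short limits the risk of losing primary ratings.

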There will be check-ins with the study participants every two weeks conducted through the participant's preferred communication method (i.e., phone call or video call) to answer questions and ensure participants are adhering to protocol requirements. Participants will be asked to keep a paper calendar for daily notes of side/adverse effects and study barriers. The paper calendar will be mailed back to the RA after study completion, or a photo of the paper calendar will be sent attached to an email to the RA. Treatment compliance data and rates of side effects will be collected in the two groups. Collection of compliance will occur through a nightly log of compliance, which the participants will receive via REDCap from the research team and fill out throughout the study.

3.f Prior and Concomitant Therapy

Participants will not qualify for the study if they are on any concomitant therapy for snoring not assigned by the study team. Participants who have tried prior therapy for the treatment of snoring will be eligible for the study. Information will be gathered on their use of prior or current therapies when determining study eligibility.

3.g Packaging

All packing of material will consist of the consumer packaging for all interventions except for the Mometasone. AdvancedRx will ship the participants the Mometasone via UPS or FedEx delivery directly to the participant's home.

3.h Blinding of Intervention

The Principal Investigator will conduct a pre-randomization visit with all participants in which he will explain both interventions to the participants and conduct a physical

exam. The physical exam will ensure the participants are in adequate physical health to tolerate both interventions and lack nasal polyps, temporomandibular joint disorder, and structural abnormalities. After this, the Principal Investigator will leave the visit and the other members of the study team will randomize the participants. This blinds the Principal Investigator to the intervention.

Before data analysis begins, [name] will download the data and anonymize the data into “A” and “B” groups. Only [name] will know which group belongs to which. The research team will then proceed with data analysis.

3.i Receiving, Storage, Dispensing and Return

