At the baseline study visit, The RC or RA and the participant and sleeping partner will complete the demographic information and baseline measures. This includes the baseline CGI-S scale, the ESS, and the SNORE-25 or the modified SNORE-25. Then randomization of the participant will occur. Participants randomized to the MAD will be scheduled to meet with the maxillofacial physician, ideally within two weeks of randomization, to be fit with the MAD. Participants randomized to the conservative therapy will be given a roll of Johnson and Johnson Band-Aid Woven Adhesive Bandages 1" x 3", one box of Breath-Right strips (either small, medium, or large), and one Neti-Pot. The participants will receive their topical glucocorticoid prescription through the mail from AdvancedRx.

E4 Maxillofacial Visits

Participants randomized to the Mandibular Advancement Device arm of the trial will undergo additional visits with the Maxillofacial Physician. The first visit will be setup after the baseline study visit to occur within 2 weeks of the consent process. At the first visit, the maxillofacial physician will educate the participant on the device, explain the treatment plan to the participant, and take a molding of the participant's teeth at this meeting. After this, the molding and measurements will be sent to ProSomnus to have the device made, which will take 7-10 days. Once the device is received by the Maxillofacial office, a second meeting will occur. At this meeting, the maxillofacial physician will ensure the device is correct size and shape and will not create undue pain or discomfort, review proper use of the device, including self-titration of the degree of jaw protrusion, and proper care of the device. These meetings will occur during the 4-week pre-intervention period as outlined in section F2.

E5 Daily Check-ins

Every morning the sleeping partner will receive a text message asking them to complete the CGI-S for the sleeping partner (*CGI-S Sleeping Partner*). They will respond via their telephone to the single question prompt until the end of the study.

E6 Visit 2

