- Events that result in such a condition where the participants may require immediate hospitalization or increase the duration of hospitalization.
- Any events that lead to a permanent or temporary physical disability in the body of the participants. Any sort of incapacity is also regarded as SAE.
- Any events that lead to any type of congenital abnormalities. It also includes any cases of birth defects resulting from the clinical trials.
- Any events where an investigator or team of investigators finds feel that it can lead to significant hazards.

7.c Classification of Events

7c.1 Relationship

An AE or SAE may or may not be causally related to the study intervention. A causal relationship means that the intervention caused (or is reasonably likely to have caused) the AE. This usually implies a relationship in time between the intervention and the AE (e.g., the AE occurred shortly after the participant received the intervention). For all AEs, it is the responsibility of the Principal Investigator who examines and evaluates the participant to determine the relatedness of the event to the study intervention.

7c.2 Severity

Severity refers to the intensity of a specific event and is a matter of individual clinical judgment.

- Grade 1: Asymptomatic or mild symptoms; clinical or diagnostic observations only; no intervention indicated
- Grade 2: Moderate; minimal, local, or noninvasive intervention indicated; limiting age-appropriate instrumental activities of daily living (ADL)
- Grade 3: Severe; or medically significant but not immediately life-threatening; hospitalization or prolongation of hospitalization indicated; disabling; limiting self-care ADL
- Grade 4: Life-threatening; urgent intervention indicated.
- Grade 5: Death related to an AE

7c.3 Expectedness

An adverse event or suspected adverse reaction is considered "unexpected" if it is not consistent with the risk information described in this protocol or on the informed consent or is not listed at the specificity or severity that has been observed; or, if an investigator

brochure is not required or available, is not consistent with the risk information described in the general investigational plan or elsewhere in the current application, as amended.

7.d Data Collection Procedures for Adverse Events

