All adverse events and suspected adverse reactions are collected from ‘source documentation’ and the research coordinator will abstract the events. Documentation can be within Washington University Epic medical records, but at times, the research coordinator will also need to have the participant send outside source documentation.

7.e Reporting Procedures

The Principal Investigator (PI) will be responsible for ensuring participants’ safety daily and for reporting Serious Adverse Events and Unanticipated Problems to the Institutional Review Board (IRB) as required.

All SAEs will be reported immediately to the Principal Investigator upon identification.

7.f Adverse Event Reporting Period

All AEs and unanticipated problems will be reported to the IRB in a prompt and timely manner to protect other subjects from avoidable harm. The appropriate time frame for satisfying the requirement for prompt reporting will vary depending on the specific nature of the unanticipated problem. For this study, unanticipated problems that are serious adverse events will be reported to the IRB within 1 week of the investigator becoming aware of the event. Any other unanticipated problem will be reported to the IRB within 2 weeks of the investigator becoming aware of the problem.

Determining the appropriate time frame for reporting a particular unanticipated problem requires careful judgment by the Research Coordinator and the Principal Investigator knowledgeable about human subject protections. The primary consideration in making these judgments is the need to take timely action to prevent avoidable harms to other subjects.

E8 Study Outcome Measurements and Ascertainment

Participants and sleeping partners will complete the following forms using REDCap after completing the intervention:

1. Clinical Global of Impression of Improvement Scale
2. Clinical Global of Impression of Severity Scale
3. Epworth Sleepiness Scale
4. Symptoms of Nocturnal Obstruction and Related Events
5. Pittsburgh Sleep Quality Index

F Statistical Plan

F1 Sample Size Determination and Power

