Case report forms will be created as electronic documents and stored within each study participant's electronic file. Original hard-copy source documents will be electronically scanned and stored in the participant's electronic file and stored in a locked file cabinet.

G2 Records Retention

All records will be retained for a minimum of six years after completion of the study and closure with the WU IRB. Data will be stored for contribution to future research studies. Contribution for future use is optional for participation in the study

H Study Administration

H1 Participant Payment

Participants will be provided a Forte/Advarra debit card. They will receive \$30 for completing each set of surveys associated with the study. As such, a participant may receive \$60 total. This will be payable to the participant upon completion of the study. If participants do not complete all requirements, they will be paid proportionally for the work they have completed. Participants will be able to keep all items received as part of their respective treatment arm. The sleeping partner will be paid an additional \$25 for responding to > 80% of the texts. If they respond to > 50% of the texts they will receive \$10. If the sleeping partner's response rate is <50% they will not be compensated for the texts.

H2 Study Timetable

Participants will be in the study for a total of eight weeks. Given the volume of patients seen at the Adult Division of the Department of Otolaryngology-Head & Neck Surgery and the Sleep Medicine Center for assessment of snoring, we anticipate it will take one year to complete enrollment, intervention, and analysis.

	Months											
	1	2	3	4	5	6	7	8	9	10	11	12
Enrollment and Baseline Assessment												
Randomization												
Pre-intervention period									1			
4 week intervention treatment												
End of participation assessment												
Data analysis and Manuscript preparation												

*Pre-intervention period is the 4-week period prior to the intervention where the MAD will be adjusted or the Mometasone nasal rinse is ongoing.

I Publication Plan

We plan to analyze accumulated data throughout the month of May 2023 and publish the results by the end of June 2023. This data includes the analysis of the CGI-I, CGI-S, SNORE-25, and ESS as well as a discussion of the potential adverse effects associated with Mandibular Advancement device and standard therapy for treatment of non-apneic snoring.

J Attachments

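### Adverse events are defined by drug use although the test arm is a device, and section 7.d does not name the harm sources that cover both arms

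*Combined protocol and SAP*

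**What the plan says.** Definition (7.b): "Adverse event (AE) means any untoward medical occurrence associated with the use of a drug in humans, whether or not considered drug related", citing the US drug regulation 21 CFR 312.32(a). The next paragraph keeps the same scope: "symptom, or disease temporarily associated with the use of a drug, without any judgment about causality or relationship to the drug". Serious adverse events are introduced as special cases of adverse events, so they inherit that scope.

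Relatedness (7c.1) is framed differently: "An AE or SAE may or may not be causally related to the study intervention".

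Collection (7.d): "All adverse events and suspected adverse reactions are collected from" source documentation, which the research coordinator abstracts. The hospital's electronic record is given as one possible source, and documents that the participant sends from elsewhere as another.

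Harm information elsewhere: under compliance monitoring, 3.e says "Participants will be asked to keep a paper calendar for daily notes of side/adverse effects and study barriers". It also schedules check-ins every two weeks and plans side-effect rates in the two groups. Section 2.h provides an exit interview that asks about adverse effects. Section I promises a "discussion of the potential adverse effects associated with Mandibular Advancement device and standard therapy".

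**The concern.** A trial of a device against a bundle that contains one drug has borrowed a definition written for drugs. Grading, expectedness, relatedness and reporting in section 7 all start from something being an adverse event. A rule that, taken at its word, leaves out the harms expected of the test treatment is therefore a defect at the first step.

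The second difficulty is that harms are described in two places that do not refer to each other. The section headed as the adverse event procedure describes abstraction of documents. The section on compliance describes participant-reported notes and group rates. Two coordinators following the same protocol could produce different counts: one abstracting records only, the other also coding the calendars. The published account of harms would then depend on a choice that the protocol does not make.

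**Working it through.** The documents give no adverse event rate, capture probability or harms analysis, so there is no figure to reproduce. The check is a comparison of the text.

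**Step 1: the definition against the treatments.** Components come from 3a.1 and 3a.2, listed harms from 2.f.

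| Component | Harms listed in 2.f | A drug? | Inside 7.b, read by component? |
|---|---|---|---|
| MAD | drooling, jaw-joint problems, tooth pain, tooth movement altering the bite | no | no |
| Mometasone rinse | systemic steroid absorption, worsening of cataract or glaucoma | yes | yes |
| Nasal strip | skin irritation | no | no |
| Mouth tape | skin irritation | no | no |
| Positional therapy | shoulder and hip pain | no | no |

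One of five components (1/5 = 20%) is covered. If association is instead read as mere coincidence in time with taking a drug, events in control participants while they use the rinse come back in. MAD participants receive no study drug, so device harms stay outside on either reading, unless the participant happens to take some unrelated medicine.

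**Step 2: the definition against the rest of section 7.** Section 7c.1 asks whether an event is related to the study intervention, which includes the device. Section 7c.3 judges expectedness against the risks described in the protocol, which include the device risks in 2.f. Both presuppose a wider definition than 7.b gives.

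**Step 3: the possible sources against 7.d.**

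| Source | Where | Stated purpose | Named in 7.d? |
|---|---|---|---|
| Medical record, outside documents | 7.d | abstraction of events | yes |
| Daily paper calendar | 3.e | notes of side effects and barriers; sent in after completion | no |
| Two-weekly check-in | 3.e | questions and adherence | no |
| Exit interview | 2.h, on withdrawal | adverse effects and reason for leaving | no |
| End-of-study measures | E6, E8 | none of the listed measures concerns adverse events | no |

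The last four are not arm-specific. None is tied to 7.d, and the check-in, the only regular scheduled conversation common to both arms, is not described as asking about harms.

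**Step 4: can a size be given?** Only under invented inputs. Suppose 30 participants per arm, the same true risk of 20% to 40% in both arms, and capture of 90% in one arm and 60% in the other. The false difference is risk × (0.90 − 0.60): 0.20 × 0.30 = 6 points, up to 0.40 × 0.30 = 12 points. The 95% half-width, 1.96 × √[a(1−a)/30 + b(1−b)/30], where a and b are the two observed proportions, is about 18 points (a = 0.18, b = 0.12) to 23 points (a = 0.36, b = 0.24). Swapping the capture probabilities reverses the sign. The documents supply none of these values, so this shows only that neither size nor direction can be fixed.

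**The case against.** The strongest reply is that harms are already collected evenly. The calendar and check-ins in 3.e make no distinction by arm, and the plan for group side-effect rates stands beside them, not in 7.d. Section 7.d is permissive about what counts as source documentation, and a paper calendar returned to the team could qualify. Section 7.b is regulatory boilerplate, while relatedness and expectedness work by intervention. Several entries in the serious event list refer to trial participation and not to a drug. F3 names no test of harms, and section I promises only a discussion. All of this stands, and it means that staff acting sensibly would probably record a sore jaw. It does not remove the conflict between 7.b and 7c.1, or the silence of 7.d about sources that 3.e and 2.h provide.

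A reader might go further and infer that harms are over-counted in the MAD arm, because E4 says that those participants "will undergo additional visits with the Maxillofacial Physician". The documents do not support that:

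- Both visits described in E4 fall in the pre-intervention period. The impression is taken at the first, before a device exists. At the second the finished device is checked and its use explained. Neither follows home use.
- Section 2.e mentions an initial visit to either the maxillofacial physician or the otolaryngology specialist, so controls cannot be assumed to have no specialist contact.
- The number of MAD visits is itself unsettled: 3a.1 says that only an initial visit is needed for fitting and 3.d has the device delivered then, whereas E4 describes two.
- The narrow definition would push the device count down and extra visits would push it up, so no net direction follows.

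**Conclusion.** The concern holds as a defect of definition and an unreconciled collection procedure. Taken literally, 7.b covers one of five treatment components and excludes the harms that the protocol itself lists for the test device, in conflict with 7c.1. Section 7.d leaves out the arm-neutral sources that the protocol already has. This rests on a literal reading of 7.b and on the measures named in E6 and E8; the survey forms themselves are not reproduced.

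It is not shown that the comparison of harms is biased. Any difference in capture between arms is a possibility whose size and direction the documents do not determine. The primary outcome is unaffected. The consequence is for the classification of device harms and for the side-effect rates planned in 3.e.

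**What to change.** - **7.b:** define an adverse event as any unfavourable medical event arising while any study intervention is in use, naming the device, drug, strip, tape and positional aid. Sections 7.b and 7c.1 then share one scope.
- **7.d:** name the daily calendar, the two-weekly check-ins and the exit interview as adverse event sources, with a cross-reference to 3.e and 2.h.
- **3.e:** use one identical symptom checklist at each check-in in both arms, covering the harms listed in 2.f for every component plus an open question. Make it the basis for the side-effect rates, and say how those rates will be summarised.
- **Reporting:** show events found only in medical records separately, so that unequal clinic contact cannot enter the rates.
- **2.i:** this section keeps withdrawn participants' data out of the analysis. State whether that applies to harms; otherwise the exit interview may contribute nothing to the rates.

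The cost is wording, a short form and a few minutes per contact. If check-ins run through all eight weeks (H2), that is 8/2 = 4 per participant and 4 × 60 = 240 in total. If they run only through the four treatment weeks, it is 2 × 60 = 120. No new visits are needed.
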